## **12 ADMINISTRATIVE AND LEGAL OBLIGATIONS**

### **12.1 Protocol Amendments**

Protocol amendments must be made only with the prior approval of the Sponsor or designee. Agreement from the Investigator must be obtained for all protocol amendments and amendments to the informed consent document. The regulatory authority and IEC/IRB must be informed of all amendments and give approval for any amendments likely to affect the safety of the patients or the conduct of the trial. The Investigator must send a copy of the approval letter from the IEC/IRB to the Sponsor or designee.

### **12.2 Study Termination**

The Sponsor reserves the right to terminate the study. The Investigator reserves the right to terminate their participation in the study, according to the terms of the site contract. Also, if new or emerging safety information affect the benefit/risk assessment of the clinical trial negatively, and with review and recommendation by the DSMB, the study would be terminated. The Investigator/Sponsor or designee should notify the IEC/IRB in writing of the trial's completion or early termination and send a copy of the notification to the Sponsor or designee.

### **12.3 Study Documentation and Storage**

An eCRF utilizing an Electronic Data Capture (EDC) application will be used for this study.

The Investigator should ensure that all appropriately qualified persons to whom he/she has delegated trial duties are recorded on a Sponsor-approved Delegation of Site Responsibilities Form.

Source documents are original documents, data, and records from which the patient's case report form data are obtained. These include but are not limited to hospital records, clinical and office charts, laboratory and pharmacy records, diaries, imaging, and correspondence. In this study eCRF may not be used as source documents.

The Investigator and Study Center staff are responsible for maintaining a comprehensive and centralized filing system of all study-related (essential) documentation in accordance with Section 8 of the ICH Guidelines (E6), suitable for inspection at any time by representatives from the Sponsor or designee and/or applicable regulatory authorities. Elements should include:

- Patient files containing completed case report forms, informed consents, and supporting copies of source documentation
- Study files containing the protocol with all amendments, Investigator's Brochure, copies of pre-study documentation and all correspondence to and from the IEC/IRB and the Sponsor or designee
- If drug supplies are maintained at the Study Center, proof of receipt, Study Drug Product Accountability Record, Return of Study Drug Product for Destruction, final Study Drug product reconciliation, and all drug-related correspondence

In addition, all original source documents supporting entries in the case report forms must be maintained and be readily available for the duration required by GCP or local regulatory requirements, whichever is longer.

No study document should be destroyed without prior written agreement between the Sponsor or designee and the Investigator. Should the Investigator wish to assign the study records to another party or move them to another location, he/she must notify the Sponsor or designee, in accordance with GCP.

## **12.4 Study Monitoring**

The Sponsor representative and regulatory authority inspectors are responsible for contacting and “visiting” (on-site or remote access) the Investigator for the purpose of inspecting the facilities and, upon request, inspecting the various records of the trial (e.g., case report forms and other pertinent data) provided that patient confidentiality is respected.

The Sponsor monitor or designee is responsible for inspecting the case report forms at regular intervals throughout the study to verify adherence to the protocol; completeness, accuracy, and consistency of the data; and adherence to local regulations on the conduct of clinical research. The monitor should have access to patient medical records and other study-related records needed to verify the entries on the case report forms. Source data should be attributable, legible, contemporaneous, original, and accurate (ALCOA) and must meet the regulatory requirements for recordkeeping.

The Investigator agrees to cooperate with the monitor to ensure that any problems detected in the course of these monitoring visits, including delays in completing case report forms, are resolved. Sponsor will ensure the Investigators are trained about the importance of patient retention, compliance with study procedures, and requirements for recording reason for missed data in the case report form. The Sponsor monitor or designee will ensure there is continuous oversight for compliance.

In accordance with ICH GCP and the Sponsor’s audit plans, this study may be selected for audit by representatives from the Sponsor’s Clinical Quality Assurance Department (or designees). Inspection of Study Center facilities (e.g., pharmacy, drug storage areas, laboratories) and review of study-related records will occur to evaluate the trial conduct and compliance with the protocol, ICH GCP, and applicable regulatory requirements.

To ensure the quality of clinical data a clinical data management review will be performed on patient data received by the Sponsor or designee. During this review, patient data will be checked for consistency, omissions, and any apparent discrepancies. In addition, the data will be reviewed for adherence to the protocol and GCP. To resolve any questions arising from the clinical data management review process, data queries and/or Study Center notifications will be sent to the Study Center for completion and return to Sponsor or designee.

The Principal Investigator will sign and date the indicated places on the case report form. These signatures will indicate that the Principal Investigator inspected or reviewed the data on the case report form, the data queries, and the Study Center notifications, and agrees with the content in accordance with the general investigational plan.

## **12.5 Language**

Case report forms must be completed in English. Whenever possible, the trade name rather than the generic name for concomitant medications should be recorded and, if possible, in English. Generic names are acceptable if the trade name is unknown. Combination medications should be recorded using their trade name in English if possible.

All written information and other material to be used by patients and investigative staff must use vocabulary and language that are clearly understood.

## **12.6 Compensation for Injury**

The Sponsor maintains appropriate insurance coverage for clinical trials and will follow applicable local compensation laws. Patients will be treated and/or compensated for any study-related illness/injury in accordance with the information provided in the Compensation for Injury section of the Informed Consent document.

## **14 APPENDICES**

## APPENDIX A. SCHEDULE OF PROCEDURES

Study Week	Screening A		Treatment Period																Follow up Period		
	Run-in	Qual M																			
	-4 to -2	-2 to -1	1	5 M	9 M	13 M	17 M	21 M	25/ET-L1 M,N	27/ET-L2 M,N	29 M	33 M	37 M	41 M	45 M	49 M	51/ET-L3 M,N	53/ET-L4 M,N or Tx ET M	4 M,O	8 M,O	13 M,O or Post-Tx ET M
Study Day	-28 to -15	-14 to -1	1 B	29	57	85	113	141	169	183	197	225	253	281	309	337	351	365	28	56	91
Visit and Testing Window ± Days	-28	0	-3	3	3	3	3	3	3	3	3	3	3	3	3	3	3	3	3	3	3
Informed Consent	X																				
Medical History	X																				
FSH C , TSH, free T4	X																				
Hepatitis B, C, HIV	X																				
Inclusion/Exclusion Criteria	X	X																			
Body Weight and Height D	X		X						X									X			X
Vital Signs	X		X	X	X	X	X	X	X		X	X	X	X	X	X		X	X	X	X
Physical Examination	X		X						X									X			X
12-lead ECG	X		X															X			X
Pregnancy Test E	X	X	X	X	X	X	X	X	X		X	X	X	X	X	X		X	X	X	X
Extended Urinalysis F	X		X	X	X	X	X	X	X		X	X	X	X	X	X		X	X	X	X
Chemistry G,H	X		X	X	X	X	X	X	X		X	X	X	X	X	X		X	X	X	X
Hematology H	X	X	X	X	X	X	X	X	X		X	X	X	X	X	X		X	X	X	X
Coagulation (aPTT, PT, INR)	X		X						X									X			
Lipid Panel G	X	X	X	X	X	X	X	X	X	X	X		X		X		X	X	X	X	X
HbA1c	X		X						X									X			X
hsCRP	X		X						X									X			X
Anti-drug Antibody (ADA) I			X	X		X			X				X					X			X
Plasma PK - olezarsen I			X	X		X			X				X					X	X	X	X
Archived Serum & Plasma Samples H,J			X			X			X	X			X		X		X	X			X
Adverse Events	X	X	X	X	X	X	X	X	X	X	X	X	X	X	X	X	X	X	X	X	X
Concomitant Medication	X	X	X	X	X	X	X	X	X	X	X	X	X	X	X	X	X	X	X	X	X
Diet/Life-style/Alcohol Counseling K	X		X	X		X		X	X		X		X		X			X		X	
Study Drug: SC Injection L			X	X	X	X	X	X	X		X	X	X	X	X	X					

All procedures and study sample collections are to be done pre-dose at respective visits, unless specified otherwise

**Legend**

- A Eligible patients will enter an approximately 4-week Screening Period (that may be extended to 8 weeks if assessments can't be completed within the 4-week period) that includes an at least 2-week Diet/life-style Stabilization/Run-In Period and an approximately 2-week Qualification Period
- B Day 1/Baseline assessments can be performed up to 3 days (-3 days) prior to the actual Day 1 visit, which is the day of first Study Drug dose
- C For confirmation of menopause at Screening per inclusion criteria
- D Height only required at Screening
- E Women who are not surgically sterile or post-menopausal. A serum pregnancy test will be performed during run-in and urine pregnancy tests will be performed at all other study visits
- F All tests listed in [Appendix B](#) under Extended Urinalysis should be performed, including routine urinalysis, urine microscopy, UACR, and UPCR. Urine collection for urinalysis should not be performed during menstruation.
- G Blood samples to be collected after an overnight fast of at least 10 hours. Fasting is not required for confirmatory tests, repeated uninterpretable, or missing tests, or tests taken for safety reasons
- H If the PLT, renal function, or liver enzyme tests are uninterpretable (e.g., due to clumping, hemolysis or quantity not sufficient) a repeat blood specimen should be re-drawn as soon as possible (ideally within 3 days and not later than 7 days). All PLT count, liver chemistry, or renal function results will be reviewed promptly (within 2 business days of receipt) by the Investigator. Any case of a PLT count < 50,000/mm^3 should be reported in an expedited fashion to the Sponsor
- I PK/ADA samples will be collected prior to dose administration (pre-dose) during Weeks 1-49 of the Treatment Period, and any time at the end of the Treatment Period (Week 53) and during follow up or ET visit, as specified in [Appendix C](#)
- J Serum and plasma archive samples will be collected and stored for follow-up exploration of laboratory findings, cardiometabolic disease relationship, and/or AEs (e.g., measurement of cytokine and/or chemokine levels, measurement of additional markers of kidney function, measurement of antibodies, etc.) in this or subsequent clinical studies of olezarsen. Samples may be stored up to 20 years
- K Recommended time points for qualified site personnel to reinforce compliance to diet/ life-style modifications and alcohol restrictions ([Appendix E](#))
- L Study Drug can be administered at home by patient or caregiver after receiving appropriate training
- M Assessments and procedures to be conducted by either the Study Center or by a Home Healthcare service (if available and permitted by local regulations) as arranged by the Study Center personnel. Physical Exam will be Body Assessment if conducted by a Home Healthcare professional
- N Landmark visit. For early termination landmark (ET-L) visits: Week 25 is ET-L1, Week 27 is ET-L2, Week 51 is ET-L3, and Week 53 is ET-L4
- O Weeks/days from end of treatment. End of treatment is defined as 1 dosing interval (4 weeks) post-last dose

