### **1.2. Study Endpoints**

#### **1.2.1. Primary Endpoint**

Percent change in fasting TG from Baseline at Month 6 (average of weeks 25 and 27) compared to placebo.

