## **6.2 Additional Study Assessments**

### **6.2.1 Laboratory Assessments**

Laboratory analyte samples will be collected throughout the study as per the Schedule of Procedures in [Appendix A](#). A list of these analytes is contained in [Appendix B](#).

Routine blood chemistry and lipid samples should be taken after fasting for at least 10 hours. Water and medications are not restricted during the fast, and the patient should ensure that they consume sufficient water in order to not become dehydrated.

Any confirmatory test, or test taken for safety reasons, may be taken at any time, irrespective of fasting status, but ideally no later than 7 days after the initial result is obtained.

If tests are uninterpretable (e.g., due to clumping, hemolysis or quantity not sufficient) or missing, a repeat blood or urine specimen should be re-drawn as soon as possible (ideally within 7 days).

Hematology samples will be collected monthly during the Treatment Period, and at every visit during the Follow-up Period. In the event that a hematology sample is unreportable (e.g., due to

hemolyzed or clumped blood samples), the patient's next scheduled dose should ideally not be administered until another sample is repeated and determined not to have met a PLT count stopping rule. The Investigator or designee will contact the patient to hold dosing until a new PLT count is obtained and reviewed. Use of home care provider or local laboratory (as described below) should be considered.

Investigators may, at their discretion, test specific laboratory parameters (except for those which must remain blinded e.g., lipid panel) which may be prone to clotting, clumping or hemolysis (e.g., hematology samples) at a local laboratory, in addition to the required central laboratory samples. In these instances, the local laboratory results should be recorded by the site into the electronic database. Assays which are blinded should not be locally tested and recorded into the database (e.g., lipid panel).

Blood and urine samples for renal function testing will also be collected monthly during the Treatment Period, and at every visit during the Follow-up Period, and sent to the central laboratory for analysis as per Section 8.5.2.

Liver chemistry testing will also be collected monthly during the Treatment Period, and at every visit during the Follow-up Period, and sent to the central laboratory for analysis as per Section 8.5.1.

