## **10.4 Definition of Baseline, Month 6 and Month 12**

Baseline PLT is defined as the average of all non-missing pre-dose assessments.

Baseline lipid measurements are defined as the average of the pre-dose measurement on Day 1 and all measurements from the Qualification Period. If the Day 1 pre-dose and Qualification Period measurements are all missing, then the last non-missing measurement from the Screening Period will be used as baseline.

Baseline for other measurements is defined as the last non-missing assessment prior to the first dose of Study Drug.

The Month 6 lipid assessments are defined as the average of Weeks 25 and 27 fasting assessments. The Month 12 lipid assessments are defined as the average of Weeks 51 and 53 fasting assessments. For both Month 6 and Month 12, if 1 of the 2 assessments is missing, then the non-missing assessment will be used.

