Missing visits or missing data related to COVID-19 may be listed. Additional listings may be provided for all patients impacted by COVID-19 during conduct of the study. Additional summary (s) and/or analyses may be provided if deemed necessary.

#### 4.2.2 Definition of Baseline, Month 6 and Month 12

Baseline lipid measurements are defined as the average of the pre-dose measurement on Day 1 and all measurements from the Qualification Period. If the Day 1 pre-dose and Qualification Period measurements are all missing, then the last non-missing measurement from the Screening Period will be used as baseline. For lipids other than TG, missing baseline values will be imputed using the multiple imputation method described in Section 4.9.1.4 in the SAP. Note that if on Day 1, there are multiple pre-dose assessments, then the last assessment with non-missing value will be used as the Day 1 pre-dose assessment.

The baseline for platelet is defined as the average of all assessments prior to the first dose of Study Drug.

The baseline for other measurements is defined as the last non-missing assessment prior to the first dose of Study Drug.

The Month 6 lipid assessments are defined as the average of non-missing Weeks 25 and 27 fasting assessments. The Month 12 lipid assessments are defined as the average of non-missing Weeks 51 and 53 fasting assessments. For both Month 6 and Month 12, if 1 of the 2 assessments is missing, then the other non-missing assessment will be used.

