#### 4.2.3 Analysis Visit Windows

The efficacy measures of fasting lipid panel (TG, APOC-III, VLDL-C, remnant cholesterol, TC, non-HDL-C, apoB, HDL-C, LDL-C, and ApoA-1), including the data from both scheduled and unscheduled visits, will be mapped to analysis visits according to the visit windows in [Table 1](#) below.

The intent of these visit windows is not to align with those prescribed for visit scheduling in the study protocol, but rather based on the protocol-defined target study day, to delineate mutually exclusive windows so that all efficacy assessments proximal to a particular study week can be integrated to best represent the patient's status during that period of the study. Visits after Week 53 are part of the post-treatment assessment period and will be summarized by the visit label provided in the data. No visit windows are needed for the data of post-treatment visits.

For lipid data, local lab data will not be used unless central lab assessments are not available at certain visit. When calculating the baseline and analysis endpoints, only if the data from central lab is missing, then the local lab data will be utilized. If there are multiple assessments within a visit window, the assessment nearest the target day will be used unless two assessments are equally near, in which case the average value will be used.

If a patient discontinued early from the treatment period but attended applicable landmark visits to collect efficacy assessments, then those assessments should be mapped to analysis visits and utilized in the analyses as well, unless otherwise stated.

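### Appendix A allows repeat lipid panels to be drawn without fasting, although the primary endpoint is fasting triglyceride and the SAP has no working rule to screen such values out

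*Combined protocol and SAP*

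**What the plan says.** The primary endpoint (protocol 1.2.1) is "Percent change in fasting TG from Baseline at Month 6 (average of weeks 25 and 27) compared to placebo". SAP 4.2.2 builds it from fasting samples: "The Month 6 lipid assessments are defined as the average of non-missing Weeks 25 and 27 fasting assessments". Month 12 is defined in the same way from Weeks 51 and 53. Protocol 10.4 adds that "if 1 of the 2 assessments is missing, then the non-missing assessment will be used", and SAP 4.2.2 repeats the rule.

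The sampling instructions do not agree with one another. Section 6.2.1 states "Routine blood chemistry and lipid samples should be taken after fasting for at least 10 hours" and then makes one exception: "Any confirmatory test, or test taken for safety reasons, may be taken at any time, irrespective of fasting status". For uninterpretable or missing tests it asks for a redraw as soon as possible, ideally within 7 days, and does not mention fasting. Footnote G of Appendix A, which is attached to both Chemistry and Lipid Panel, goes further: "Fasting is not required for confirmatory tests, repeated uninterpretable, or missing tests, or tests taken for safety reasons".

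SAP 4.2.3 says that the fasting lipid panel, "including the data from both scheduled and unscheduled visits, will be mapped to analysis visits". Within a window it takes the result nearest the target day, and it uses a local laboratory value only where the central one is missing. It does not say how fasting status is established or what happens to a non-fasting result. The baseline definition (protocol 10.4, SAP 4.2.2) averages the Day 1 value and every Qualification value without using the word fasting.

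**The concern.** A site that follows footnote G may redraw a spoiled or missed lipid panel from a patient who has eaten. The waiver suits safety chemistry, where a quick repeat matters more than the fasted state. It does not suit an endpoint defined on fasting TG, which food is expected to raise.

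If the redraw is analysed, a fed value enters the Month 6 or Month 12 mean, the responder endpoint at 150 mg/dL, or the baseline in the denominator. If it is set aside as non-fasting, the patient's visit has produced nothing usable. In neither case does the plan say in advance which happens, so someone would have to decide it from the data.

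**Working it through.** **The plan's own figure.** The only design figure nearby is the power statement (protocol 10.2): 33 per olezarsen arm, 22 on placebo, difference 60, SD 73, two-sided alpha 0.05. The standardised difference is 60 / (73 × √(1/33 + 1/22)) = 2.986. Normal power is Φ(2.986 − 1.960) = 84.8%, and the noncentral t with 53 df gives 83.4%, against a stated figure of about 80%. The stated figure is slightly conservative. The point here does not depend on it.

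**Can a redraw reach the analysis?** Target days and windows are from SAP Table 1, and the 7 days from Section 6.2.1.

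| Visit | Target day | Target + 7 | Window |
|---|---|---|---|
| Week 25 | 169 | 176 | 156–176 |
| Week 27 | 183 | 190 | 177–190 |
| Week 51 | 351 | 358 | 331–358 |
| Week 53 | 365 | 372 | 359–379 |

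All four redraws fall inside their window. When the scheduled sample gave no result, the redraw may be the only value there. If the spoiled sample was itself taken 3 days late, a redraw 7 days after it (days 179, 193, 361, 375) stays in its own window only at Week 53.

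**If fed values are kept.** The documents give neither the share of single samples that are non-fasting redraws (q) nor the fed-to-fasting TG factor (f). I assume q = 1–10% and f = 1.10–1.50. With r the ratio of TG to baseline (1.0 on placebo and 0.4 on olezarsen, from the design assumption), the shift in an arm mean is 100 × q × (f − 1) × r points.

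| q | f | Placebo | Olezarsen | Difference |
|---|---|---|---|---|
| 1% | 1.10 | +0.10 | +0.04 | −60.06 |
| 5% | 1.25 | +1.25 | +0.50 | −60.75 |
| 10% | 1.50 | +5.00 | +2.00 | −63.00 |

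An equal proportional error therefore slightly enlarges the apparent effect. If only olezarsen samples were affected, the difference would be −59.96 to −58.0, and normal power at 33/22 would fall from 84.8% to no lower than 82.3%. If only placebo samples were affected, the extreme corner would be −60 − 5 = −65.

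For one patient with one of two samples fed, the shift is 100 × r × (f − 1) / 2: +5 to +25 points at r = 1.0 and +2 to +10 points at r = 0.4.

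**Responder endpoint.** A patient with fasting TG 140 mg/dL and one of two draws 15% high averages (140 + 161) / 2 = 150.5 and is no longer a responder.

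**Baseline.** Assume two baseline samples and the extreme q = 10%, f = 1.50. One sample is fed in 2 × 0.10 × 0.90 = 18% of patients (percent change based on r / 1.25) and both in 1% (r / 1.50). The placebo mean shifts by 100 × [0.18 × (0.80 − 1) + 0.01 × (0.667 − 1)] = −3.9 points and the olezarsen mean by 0.4 × (−3.9) = −1.6. The difference becomes −60 − 1.6 + 3.9 = −57.7. This is a similar size in the opposite direction.

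**If fed values are excluded.** With independent losses, at least one Month 6 sample is affected in 1 − (1 − q)² = 2.0% to 19.0% of patients (about 3 to 29 of 152). These patients keep their other sample. Both are lost in q² = 0.01% to 1.0% (about 0.02 to 1.5 of 152), and only these need imputation.

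**The case against.** The strongest reply is that the text already excludes such values. Month 6 and Month 12 are averages of fasting assessments, and the mapping sentence in SAP 4.2.3 has the fasting lipid panel as its subject, so a fed redraw is not eligible. Footnote G permits a non-fasting redraw but does not require one, and fasting status may be captured in the eCRF or laboratory instructions, which are not available here. This stands as a reading of the endpoint definitions. It does not supply the working rule, it does not reach the baseline definition, and on this reading footnote G authorises a sample that the endpoint cannot use.

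Two stronger readings are tempting, and the documents do not support them. A reader might infer that every such redraw is either biased or imputed. The rule for a missing member of the pair provides a third route: the other sample is used, and imputation starts only when both are lost. A reader might also infer that an olezarsen patient who loses both Month 6 samples is imputed back to placebo level. SAP 4.9.1.4 describes the jump-to-reference fallback for patients who discontinue treatment, and for values after the last observed one. A patient still on treatment normally has panels at Weeks 29, 37 and 45, so a Month 6 gap is not after the last observed value, and step 3 of the imputation code would not remove the own-arm imputation.

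Finally, redraws in a blinded trial have no stated reason to differ by arm. That is a fair ground for taking the equal-rate case as the main one.

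**Conclusion.** The inconsistency is real. Footnote G gives a permission for lipid redraws that Section 6.2.1 does not give and that a fasting endpoint cannot accommodate, and the SAP has no operating rule to settle the result. A reader might go on to infer that the primary endpoint is undermined. The figures do not support that: with 1–10% of samples affected equally in all arms and fed TG 10–50% above fasting, the 60-point design difference moves by at most about 3 points, and a fed baseline works in the opposite direction. Both ranges are assumptions, because the documents give no redraw rate and no fed-to-fasting factor. Individual values can move more, which matters mainly for patients near 150 mg/dL. This is a gap in sampling and data-handling rules, worth closing because closing it is cheap. It does not threaten the primary conclusion.

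**What to change.** - **Protocol:** reconcile footnote G with Section 6.2.1 by exempting the lipid panel from the redraw waiver. Lipid redraws at baseline and landmark visits should follow the 10-hour fast and, at landmark visits, fall within the SAP analysis window. The ±3-day visit window is not the right limit, since it is tighter than the 7-day redraw allowance and would create missing data. The waiver can stay as it is for safety chemistry.
- **Data collection:** record fasting status with every lipid sample.
- **SAP 4.2.2 and 4.2.3:** state that only fasting lipid values are used for baseline, Month 6 and Month 12, whatever prompted the sample. A sensitivity analysis that includes the non-fasting values would show whether the rule matters.

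The cost is a site memo or short protocol wording and a line in each of the two SAP sections. The downside is that an occasional patient must return fasting. If sampling is already complete, the SAP lines can still be fixed before unblinding, provided fasting status can be recovered.
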